#### 17.6.1 ***Unified Dyskinesia Rating Scale (UDysRS) total score***

Change from baseline in the UDysRS total score to Visit 6 (Day 28) and Visit 7 (Day 42) respectively will be summarized using descriptive statistics. A Wilcoxon signed-rank test will be used to assess statistically significant differences between active treatment and placebo for each time point. The same analysis will be done for UDysRS total objective score Part III and IV only.

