**Table 2 Changes in the planned statistical analyses**

Change category	Timing of change	Description of change	Reason for change	Responsible for change
Change in the SAP compared to the CSP	Prior to DBL	The safety analysis set has been omitted.	Safety evaluations based on FAS is considered sufficient.	[name]
Change in the SAP compared to the CSP	Prior to DBL	The Chi2 test for the ON Time Without Troublesome Dyskinesia analysis has been replaced with a linear mixed model approach.	The CSP prescribes that a chi-square test be performed for ON Time Without Troublesome Dyskinesia data for the whole study period. As there are multiple measurements per patient and visit, it is not clear how this can be implemented. Hence a shift to a mixed model approach has been adopted.	[name]
Change in the SAP compared to the CSP	Prior to DBL	Wilcoxon signed rank tests have been replaced with linear mixed modeling with a non-parametric back-up plan should model assumptions fail.	In order to use all available data in the same model, potentially resulting in higher power in the analyses, a mixed model approach has been adopted instead.	[name]
Change in the SAP compared to the CSP	Prior to DBL	The Kinesia 360 wearable dyskinesia assessment system and PD home dyskinesia diary data for up to 4*24 hours prior to Visit 6 and 7 is included in the analyses.	The CSP prescribes data from only up to 2*24 hours to be used in Kinesia 360 wearable device and home diary analyses. However, using the cut-off point of 4*24 hours prior to Visit 6 and 7 respectively was deemed medically acceptable, whereas at the same time minimizing the amount of missing data in the corresponding analyses.	[name]

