### 9.2 Analysis of secondary endpoints

#### 9.2.1 *Statistical inferential analysis of efficacy endpoints*

Absolute change from baseline in efficacy endpoints (secondary and exploratory endpoints) will generally be analysed using a linear mixed model with treatment, visit and the interaction

treatment\*visit as fixed categorical effects and subject within treatment as a random effect. The baseline value of the dependent variable will be included in the model as a continuous covariate, to account for possible differences in change from baseline outcomes due the starting baseline level. Visit will be modelled as a repeated effect. Kenward-Roger's approximation for degrees of freedom will be used.

Providing a significant type III F-test for the interaction effect treatment\*visit, differences between least square estimates of NLX-112 and placebo for the same visit (i.e. from the interaction term treatment\*visit, where visit is the same for both NLX-112 and placebo) will be estimated and the corresponding p-value will be presented in tables. In addition, differences between least square estimates of each post-baseline visit and baseline for NLX -112 and placebo respectively (i.e. from the interaction term treatment\*visit, where treatment is the same for the post-baseline and the baseline visit) will be estimated and the corresponding p-value will be presented in tables.

The model proposed above will be used for FAS and is valid, as long as the underlying data is missing at random (MAR). As a sensitivity analysis, the model will also be run for PPS, serving as a validity check for the main FAS analysis. The sensitivity analysis will be a complete case analysis, i.e., only patients with no missing data for the dependent variable will be used.

Model diagnostics, for example Shapiro-Wilk's test for a normally distributed residual term and Leven's test for the homoscedasticity assumption of the residual term as well as Q-Q plots and plotting residuals vs. predicted values, will be performed. If model assumptions are deemed to be violated, an attempt will be made to transform the dependent variable in order to fulfil model diagnostics.

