A box-cox model will be used to find the most appropriate transformation of data. Lambda values between -3 and 3 will be tested using increments of 0.25. The dependent variable will be transformed accordingly, and the linear mixed model rerun on transformed data. Subsequently, the same model diagnostics as described above will be performed. If model assumptions are deemed to be violated, the linear mixed model approach will not be further pursued for the corresponding dependent variable.

If transforming data according to the above method fails, the analysis will be done using non-parametric methods. A Wilcoxon rank sum test will be used to assess statistically significant differences between active treatment and placebo for relative change from baseline in efficacy endpoints for all post-baseline visits respectively. Furthermore, a Wilcoxon signed rank test will be performed for each post-baseline visit and baseline for NLX -112 and placebo respectively to assess statistically significant differences between each post-baseline visit and baseline for each treatment separately.

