### 10.2.3 Secondary endpoint(s)

#### 10.2.3.1 Unified Dyskinesia Rating Scale (UDysRS) total score

**Table UD 1 UDysRS total score for all Parts (Full analysis set)**

Result category	Assessment timepoint		NLX-112 (N=XX)	Placebo (N=XX)	Total (N=XX)
Measured value	[Assessment timepoint 1]	n	xx	xx	xx
		Mean (SD)	x.xx (x.xx)	x.xx (x.xx)	x.xx (x.xx)
		Median (Min, Max)	x.xx (x.x, x.x)	x.xx (x.x, x.x)	x.xx (x.x, x.x)
	[Assessment timepoint 2]	n	xx	xx	xx
		...	...	...	...
Absolute change from baseline	[Assessment timepoint 2]	n	xx	xx	xx
		Mean (SD)	x.xx (x.xx)	x.xx (x.xx)	x.xx (x.xx)
		Median (Min, Max)	x.xx (x.x, x.x)	x.xx (x.x, x.x)	x.xx (x.x, x.x)
	[Assessment timepoint 3]	LMM a p-value	xxxxx b	xxxxx c	xxxxx d
		n	xxxxx	xxxxx	xxxxx
		...	...	...	...
Relative change from baseline (%)	[Assessment timepoint 2]	n	xx	xx	xx
		Mean (SD)	x.xx (x.xx)	x.xx (x.xx)	x.xx (x.xx)
		Median (Min, Max)	x.xx (x.x, x.x)	x.xx (x.x, x.x)	x.xx (x.x, x.x)
	[Assessment timepoint 3]	n	xxxxx	xxxxx	xxxxx
		...	...	...	...

a) Linear mixed model (LMM) with treatment, visit and the interaction treatment\*visit as fixed categorical effects and subject within treatment as a random effect. The baseline value of the dependent variable has been included in the model as a continuous covariate. Kenward-Roger's approximation for degrees of freedom will be used.

b) p-value for the difference between NLX-112 at the assessment timepoint and at baseline.

c) p-value for the difference between placebo at the assessment timepoint and at baseline.

d) p-value for the difference between NLX-112 and placebo absolute change from baseline at the assessment timepoint.

Data based on the Full analysis set. The session marked as most severe for Part III and IV have been used. For Part III, the highest score for each individual questionnaire item has been used. All UDysRS item scores for Part I, II, III and IV have been summarized pre patient and assessment timepoint and used as input data to the table. N: Number of observations. SD: Standard deviation. NC: Not calculated - number of evaluable observations less than 3. NA: Not available - no evaluable observations. SAS program: [PROGRAM NAME].sas. Run by: [USERNAME] YYYY-MM-DDTHH:MM:SS. Data extracted at: YYYY-MM-DDTHH:MM:SS

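### The NLX-112 versus placebo difference at each visit is estimated only if the treatment-by-visit interaction is significant, and the SAP does not say which visits that test covers

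*SAP*

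**What the plan says.** SAP 9.2.1 analyses absolute change from baseline in a linear mixed model with treatment, visit and their interaction as fixed effects and subject within treatment as a random effect. Visit is also a repeated effect. The same-visit NLX-112 versus placebo contrasts come with a condition: "Providing a significant type III F-test for the interaction effect" of treatment by visit. The SAP does not say what is reported if that test is not significant. It is also unclear whether the condition extends to the within-arm contrasts in the next sentence.

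The condition appears nowhere else:

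- Protocol 17.6.1: "A Wilcoxon signed-rank test will be used to assess statistically significant differences between active treatment and placebo for each time point".
- SAP Table 2, on the change of method: "Wilcoxon signed rank tests have been replaced with linear mixed modeling with a non-parametric back-up plan should model assumptions fail". It does not mention an interaction test.
- Table UD 1, footnote d: "p-value for the difference between NLX-112 and placebo absolute change from baseline at the assessment timepoint".
- The fallback in SAP 9.2.1: "A Wilcoxon rank sum test will be used to assess statistically significant differences between active treatment and placebo", at all post-baseline visits.

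No section lists the levels of visit or names a covariance structure, and the indirect evidence conflicts. The within-arm contrasts are taken from the interaction term "where treatment is the same for the post-baseline and the baseline visit", and Table UD 1 footnote b describes a "p-value for the difference between NLX-112 at the assessment timepoint and at baseline". Both lean towards baseline as a visit level. Against that, the response is already a change from baseline, and "The baseline value of the dependent variable will be included in the model as a continuous covariate", which suggests Day 28 and Day 42 only.

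**The concern.** A treatment-by-visit interaction tests whether the treatment effect differs across the visits in the model. If those are Day 28 and Day 42, a drug that works equally well at both produces no interaction, so the comparison of interest would usually not be estimated. A sustained benefit is the pattern most likely to be lost. Near-equal effects are plausible: the scheduled dose is 1.75 mg/day on Days 25–28 and 2 mg/day on Days 29–42, and patients returned to a lower tolerated dose may be on the same dose at both visits.

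If baseline is also a level, every patient contributes a change of exactly zero there. The interaction then does respond to a drug effect, but those zero-variance rows distort the error term.

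SAP 5.1 rests any inference of superiority on these tests, and the Day 42 change in UDysRS total score is the first-listed secondary endpoint. Two programmers could follow the same SAP and report different Day 42 results.

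A related gap concerns CGI-C, which SAP 9.2.5 sends to this model. Protocol Table 8.1-1 has CGI-S at baseline and CGI-C only afterwards, so CGI-C has no baseline value to serve as a covariate or as a baseline row.

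**Working it through.** The plan gives no power, effect size or SD (SAP 5.2), so there is no figure to reproduce.

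**Inputs from the documents:** 16 versus 8 patients (SAP 4.3); two-sided 5% tests (SAP 5.7); UDysRS at baseline, Day 28 and Day 42 (SAP 9.2.2).

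**Assumptions:** complete data; SD of change 1 at each visit; Day 28–Day 42 correlation ρ of 0.5 to 0.8; no covariate unless stated. Effects are in SD units.

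**Day 42 contrast without the condition.** This is a two-sample t-test on 22 df with noncentrality d / √(1/16 + 1/8) = d / 0.433. For d = 1.0 that is 2.31, power 60%; for d = 1.27, 2.93, power 80%; for d = 1.5, 3.46, power 91%.

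**Reading A: Day 28 and Day 42 only.** With two visits and complete data, the interaction test is a two-sample t-test (22 df) on each patient's Day 42 minus Day 28 change. A common-slope baseline covariate cancels. The noncentrality is (d42 − d28) / [√(2(1 − ρ)) × 0.433]. For equal effects it is zero, so the condition is met in 5% of trials however large the effect. For 0.5 then 1.0 SD it is 0.5 / (1 × 0.433) = 1.15 at ρ = 0.5 (met in 20%) and 0.5 / (0.632 × 0.433) = 1.83 at ρ = 0.8 (met in 42%). The joint probabilities below are simulated, with at least 40,000 trials per scenario; ranges are over ρ.

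| Effect at Day 28, Day 42 | Condition met | Day 42 significant and reported | Day 42 significant, no condition |
|---|---|---|---|
| 1.0, 1.0 | 5% | 3% | 60% |
| 1.5, 1.5 | 5% | 4% | 91% |
| 0.875, 1.0 (ratio 1.75/2) | 6–7% | 4–5% | 60% |
| 0.8, 1.0 | 7–11% | 6–8% | 60% |
| 0.5, 1.0 | 20–42% | 17–29% | 60% |
| 0.25, 1.27 | 61–94% | 55–77% | 80% |

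With a baseline covariate (correlation 0 to −0.4 with change; 20,000 trials per scenario), the 1.0, 1.0 row becomes 3% against 58–65%.

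**Reading B: baseline also a level, compound symmetry.** This was simulated as a split-plot analysis on rows 0, Day 28 and Day 42, with interaction F on 2 and 44 df and Satterthwaite df standing in for Kenward-Roger. For an equal 1.0 SD effect:

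- The condition is met in 63–68% of trials.
- It lowers rejection by the model's own Day 42 contrast from 75% to 59–65%.
- Judged by a valid Day 42 t-test instead, the fall is from 60% to 53–58%.
- Under the null, the model's Day 42 contrast rejects 11% without the condition and 3–5% with it.

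The 11% can be checked by hand. The pooled single-visit variance has expectation (0 + 1 + 1)/3 = 2/3 of the true Day 42 variance, so the t statistic is inflated by √1.5 = 1.22. With 22 df the critical value 2.074 acts like 2.074 / 1.225 = 1.69, a rejection rate of 10.5%; with 66 df it is 10.8%. An unstructured matrix cannot be fitted to the baseline rows because their variance is zero.

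**What survives.** Table UD 1 still gives n, mean and SD by arm, so a raw Day 42 difference can be derived. Its 95% half-width would be t(0.975, 22) × √(1/16 + 1/8) = 2.074 × 0.433 = 0.90 SD.

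**The case against.** The strongest reply is that the severe figures belong to Reading A, while the wording on within-arm contrasts and footnotes b and c fits Reading B better: a contrast with the baseline visit does not exist unless baseline is a level. On Reading B the text as written does limited harm, and the 11% arises only if someone removes the condition without fixing the visit list. That is right, and it is why the two points must be settled together. It does not settle the reading, because a change-from-baseline response with a baseline covariate points the other way.

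Second, SAP 9.2.1 goes on to residual diagnostics, Box-Cox and then an unconditional rank sum test. Under Reading B the zero-variance baseline rows would often trip Levene's test. Grouped by visit, in 3,000 simulated trials per scenario, it rejected in 100% on marginal residuals, and on conditional residuals in about 95%, 78–80% and 30% at correlations 0.5, 0.65 and 0.8. The Reading B figures may therefore describe a path that is often abandoned. This stands as a limit on those figures. It also means that residual diagnostics would decide whether Day 42 is tested unconditionally, which is no better.

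Third, the model contains a treatment main effect, the natural term for a constant effect. True, but the SAP gives no rule for reporting it.

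Fourth, efficacy is secondary, SAP 5.8 calls the tests explorative, SAP 5.1 calls significant findings indicative, and a table shell need not repeat conditional logic. All fair, and they limit the weight. But an exploratory trial depends on its estimates, and the condition buys no multiplicity control, since SAP 5.8 adjusts for nothing.

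**Conclusion.** The concern holds. The condition is in SAP 9.2.1, is absent from the protocol, Table 2 and the shell, and does not apply to the fallback. Its effect cannot be determined from the SAP because the visit levels and covariance are not stated. On Reading A with equal effects it nearly eliminates the Day 42 comparison (3% against 60% at 1.0 SD; 4% against 91% at 1.5 SD). Equal effects are the worst case, and the loss shrinks as the Day 42 effect outgrows the Day 28 effect. On Reading B with compound symmetry the loss is small to moderate, but the underlying contrast is anti-conservative once the condition is removed. The text is certain. The percentages depend on the assumed effects, SD, correlations and complete data. Given the exploratory role of efficacy and the surviving descriptive tables, this should be fixed before database lock but does not undermine the trial's primary objective.

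**What to change.** In SAP 9.2.1:

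- State that the model uses post-baseline visits only (Day 28 and Day 42). Say whether Visit 9 enters the UPDRS model, since Table UP 1 asks for every visit with UPDRS data.
- Name the covariance structure, for example unstructured over the two visits, and drop the then redundant random subject term.
- Delete the interaction condition. Always report the NLX-112 minus placebo LS-mean difference with 95% CI and p-value at Day 42 and Day 28, and keep the interaction test as descriptive.
- Take within-arm change from each arm's LS mean at the visit, and align Table UD 1 footnotes b and c.
- For CGI-C, drop the baseline covariate or name CGI-S as the covariate, and state the value that the within-arm test is against.
- Record the change in SAP Table 2.

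The condition and the visit list must be changed together. The cost is a few sentences, one Table 2 line and minor shell edits, with no new data. More nominal p-values will be reported per endpoint, which SAP 5.8 already leaves unadjusted.

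### The SAP's mixed model for change from baseline also uses baseline as a visit level, where every change is zero; under a homogeneous covariance this makes the Day 42 between-arm standard error about 14–18% too small

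*SAP*

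**What the plan says.** SAP 9.2.1 defines the response: "Absolute change from baseline in efficacy endpoints (secondary and exploratory endpoints) will generally be analysed using a linear mixed model". Fixed effects are treatment, visit and their interaction. It adds "subject within treatment as a random effect" and the baseline score: "The baseline value of the dependent variable will be included in the model as a continuous covariate". On the error structure it says only "Visit will be modelled as a repeated effect", with no covariance structure named, and "Kenward-Roger's approximation for degrees of freedom will be used".

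Two sets of contrasts follow. Between-arm differences at the same visit are estimated only if the type III F-test for treatment-by-visit is significant. Within-arm contrasts are "differences between least square estimates of each post-baseline visit and baseline for NLX -112 and placebo respectively", drawn from the same interaction term, "where treatment is the same for the post-baseline and the baseline visit". Footnote b of Table UD 1 repeats this, "p-value for the difference between NLX-112 at the assessment timepoint and at baseline", and footnote c does the same for placebo.

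SAP 5.7 sets a two-sided 5% level. SAP 5.1 rests any inference of superiority on these tests and also calls significant findings indicative rather than confirmatory. SAP 5.8 makes no multiplicity adjustment.

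**The concern.** A treatment-by-visit contrast against the baseline visit exists only if baseline is a level of visit. When the response is change from baseline, that level holds a constant: zero for every patient in both arms. These rows say nothing about treatment, but they enter the variance estimate as if they were perfectly precise observations. A model with one common variance then understates the variability at Days 28 and 42 and reports p-values for the between-arm contrast that are too small.

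Day 42 UDysRS total score is the first-listed secondary endpoint, and SAP 9.2.2 to 9.3.5 send nearly every other efficacy endpoint through the same section. A p-value labelled as a 5% test should behave as one, even in an exploratory analysis.

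**Working it through.** **Inputs from the documents.** 16 and 8 patients (Protocol 8.1). UDysRS at baseline, Day 28 and Day 42 (SAP 9.2.2). Two-sided 5% (SAP 5.7). Model terms as in SAP 9.2.1.

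**Assumptions.** The documents give no SD, correlation or covariance structure. The main runs use normal scores, equal SD at each visit, baseline-to-post correlation 0.3–0.8, Day 28-to-Day 42 correlation 0.3–0.9 and no dropout. Satterthwaite degrees of freedom stand in for Kenward-Roger.

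**Step 1: share of constant rows.** 24 × 3 = 72 rows, of which 24 are zero by definition: 24/72 = one third.

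**Step 2: analytic check.** Take a common variance and no covariate, and let the change have variance s² at each post-baseline visit. The pooled variance is (0 + s² + s²)/3 = (2/3)s², so the SE is multiplied by √(2/3) = 0.816. A nominal 5% t-test then rejects with probability P(|t| > 0.816 × t₀.₉₇₅):

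| df | Actual rate |
|---|---|
| 21 | 10.4% |
| 40 | 10.7% |
| 60 | 10.8% |

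**Step 3: full model, no effect at any visit, Day 42 between-arm contrast taken alone.**

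| Model | Rejection rate |
|---|---|
| Zero rows in, random intercept / compound symmetry | 9.0–10.5% |
| Zero rows in, AR(1) | 9.7–11.1% |
| Zero rows in, post-baseline SDs unequal (ratio 1.2–1.3) | 6.7–14.7% |
| Visits 6 and 7 only, equal SDs | 4.9–5.1% |
| Visits 6 and 7 only, unequal SDs, homogeneous covariance | 2.5–7.7% |

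The model SE with the zero rows is about 0.82–0.86 of the true SE, so 14–18% too small. The stated 5% is recovered only in the fourth row. The last row shows that dropping the zero rows is not enough unless unequal variances are allowed.

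**Step 4: add the SAP's F-test condition (zero rows in).** With no effect at any visit, the F-test is significant in 4.9–7.0% of trials. The F-test and the Day 42 contrast are both significant in 2.6–5.4%, up to 6.5% at extreme correlations. With a true Day 28 effect of 1.0–1.5 residual SD and none at Day 42, the condition was met in 56–99% of trials, and a significant Day 42 difference followed in 8.0–11.0% of all trials.

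**Step 5: unstructured covariance.** As the baseline-row variance is taken from 10⁻¹ to 10⁻⁸, −2 REML log-likelihood falls from −33 to −371 with no minimum. The likelihood is unbounded and the model cannot be fitted.

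**Step 6: within-arm contrasts.** Their null rejection rate is 3.6–4% when the two changes correlate below 0.5, about 5% at 0.5, 7–9% at 0.7–0.88 and about 10% near 0.95. The error goes in either direction.

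**The case against.** A reader might infer that the plan's Day 42 test has a 9–11% false-positive rate outright. It does not: the F-test condition is part of the procedure and holds the rate near 3–5% when nothing works at any visit. That stands, but the protection fails once there is an effect at Day 28, and the condition does not repair the SE behind any p-value that is reported.

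The inflation also needs a homogeneous covariance, which the SAP does not name. That stands as a condition on the figures. It does not rescue the model, because the unstructured alternative fails to fit.

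The literal reading can be questioned. Table UD 1 has no baseline row under absolute change. Table CG 1 carries the same footnote markers for CGI-C, which has no baseline value, so they may be template text. A programmer could fit Visits 6 and 7 and test LS mean change against zero. That is possible and sensible, but it is not what 9.2.1 says.

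A further tempting reading is that the SAP's Levene check must fail, so that the model is always abandoned. The SAP states neither the residual type nor the grouping. With zero rows in, failure ranged over 70–100% for marginal residuals by visit, 0.3–100% for conditional residuals by visit and 3–20% for conditional residuals by treatment. The check may be tripped, and no transformation makes a constant vary, but failure is not certain. Where the model is dropped, its p-value is not the one reported, so the two harms should not be added together.

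Finally, the primary objective is safety, and SAP 5.1 and 5.8 declare these tests indicative and exploratory. That limits the consequence without making the rule right.

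**Conclusion.** The concern holds in a bounded form. As worded, SAP 9.2.1 and Table UD 1 footnotes b and c put rows that are zero by definition into the response. Under a random-intercept, compound-symmetry or AR(1) covariance with equal visit SDs, the Day 42 between-arm SE is about 14–18% too small, and that contrast alone runs at about 9–11%. Under the full procedure the rate is about 3–5% with no effect anywhere and about 8–11% when a Day 28 effect satisfies the F-test condition. Under an unstructured covariance there is no usable fit.

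Two limits apply. The claim is not that every SE is too small, since the within-arm tests can be conservative. CGI-C lies outside this mechanism because it has no baseline value. All rates rest on assumed correlations, slopes and SDs. This is an incorrect rule in an exploratory analysis, not merely missing detail, and it should be corrected.

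**What to change.** In SAP 9.2.1:

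- State that only the post-baseline visits (Visits 6 and 7) are levels of visit, and that baseline enters only as the covariate.
- Replace the post-baseline-minus-baseline contrast by each arm's LS mean change at that visit, tested against 0, with its 95% CI. Reword Table UD 1 footnotes b and c to match.
- Remove the treatment-by-visit F-test condition on the between-arm visit contrasts in the same edit. With two visit levels it would test whether the effect differs between Day 28 and Day 42. An effect equal at both visits would meet the condition only about 5% of the time, and the null rate for a reportable Day 42 difference would fall to about 0.5–1.3%.
- Name a covariance structure that allows unequal visit variances, for example unstructured over the two visits in place of the separate random intercept.

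The cost is SAP wording and minor code. Nominal p-values for the Day 42 contrast will become less favourable.

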## 9.8 Patient withdrawal

### 9.8.1 *General withdrawal criteria*

Patients are free to discontinue their participation in the study at any time and for whatever reason without affecting their right to an appropriate follow-up investigation or their future care. If possible, the reason for withdrawal of consent should be documented.

Patients may be discontinued from the study at any time at the discretion of the Investigator.

Reasons for discontinuation include:

- Patient decision (withdrawal of consent)
- Severe non-compliance to study protocol procedures, as judged by the Investigator and/or Sponsor
- Permanent discontinuation of IMP. Temporarily treatment interruptions of  $\geq 3$  days may result in study discontinuation as judged by the Investigator and Sponsor.
- Patient is lost to follow-up. If a patient misses a scheduled visit and is repeatedly unable to be contacted, the patient will be withdrawn from the study.
- Significant AEs posing a risk for the patient, as judged by the Investigator and/or Sponsor
- Withdrawal of informed consent to the use of biological samples
- Pregnancy
- Death - Request an autopsy report
- Use of prohibited medication as judged by the Investigator and/or Sponsor
- The patient exhibits serious suicidality, in the clinical judgement of the investigator or according to criteria below:
  - Any suicidal behavior (i.e. actual attempt, interrupted attempt, aborted attempt, or preparatory acts or behavior)
  - Any suicidal ideation of type 4 or 5 in the C-SSRS (i.e. active suicidal thought with intent but without specific plan, or active suicidal thought with plan and intent)

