#### 4.3 Randomization and number of subjects

On Day 1, patients were randomized to receive either NLX-112 or placebo with the ratio 2:1 for active treatment to placebo. This will give approximately 16 patients who received NLX-112 and 8 patients who received placebo in the study. In addition, approximately the same ratio was intended to be attained within each site. The study used competitive enrolment between 5 sites.

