### 5.2 Sample size calculation

No formal sample size calculation has been performed. The sample size of 24 patients is considered sufficient to evaluate the primary objective and to allow for a preliminary efficacy evaluation.

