## 5.7 Significance level

All hypothesis testing will be two-sided, using a 5% significance level ( $\alpha=0.05$ ).

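### The complete-case per-protocol run named as the validity check of the FAS mixed model cannot check its missing-at-random assumption

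*SAP*

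**What the plan says.** SAP 9.2.1 analyses change from baseline with a linear mixed model on the FAS and describes that model as valid under MAR. One sensitivity analysis follows: "As a sensitivity analysis, the model will also be run for PPS, serving as a validity check for the main FAS analysis". It is narrowed further, because "only patients with no missing data for the dependent variable will be used". Under SAP Table 1 the FAS is everyone randomised and dosed. The PPS also requires no major protocol violation and 75% compliance. SAP 5.9 plans no imputation in general and leaves open unspecified methods if much is missing. No analysis that departs from MAR is specified.

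The schedule of events (Protocol Table 8.1-1) places the UDysRS at Visits 2, 6 and 7 only, so there are two post-baseline values, at Day 28 and Day 42. The early-withdrawal visit shares the Visit 9 schedule, which has no UDysRS. Protocol 8.1 lets patients with intolerable adverse events during up-titration step back to a lower dose or withdraw. Protocol 9.8.1 lists many reasons for discontinuation, among them significant adverse events and "Permanent discontinuation of IMP".

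**The concern.** The check is described straight after the MAR statement, so a reader will take agreement between the two runs as support for the main result. A sensitivity analysis for missing data should relax the assumption in doubt. This one tightens it. It also changes the patient set through two post-randomisation criteria, so a gap could not be traced to missing data.

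At stake is how the secondary efficacy result is read. Agreement could be reported as robustness in the very situation where the comparison is blind. Disagreement could cast doubt on a main analysis that is sound.

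**Working it through.** **Inputs from the documents.** Allocation (SAP 4.3): "This will give approximately 16 patients who received NLX-112 and 8 patients who received placebo in the study". There are two post-baseline UDysRS visits. On sample size (SAP 5.2): "No formal sample size calculation has been performed". The plan therefore has no effect size, SD or dropout rate to reproduce, and those below are assumptions.

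**Step 1: the two estimators.** Take the model as fitted to the two post-baseline changes. With monotone dropout, the FAS likelihood estimate of the Day 42 effect is γ_T + γ_1 × α_T:

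- α_T is the baseline-adjusted treatment effect on the Day 28 change, in everyone with a Day 28 value.
- γ_T and γ_1 are the coefficients of treatment and Day 28 change in a regression of Day 42 change on treatment, baseline and Day 28 change, in patients with both visits.

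The complete-case estimate is the baseline-adjusted Day 42 effect in patients with both visits. If every patient with missing data left before Day 28, both FAS regressions use the same completers and the two estimates are algebraically identical. If some left after Day 28, the FAS fit uses their Day 28 value and the complete-case fit discards it.

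**Step 2: simulation.** Assumptions: change-score SD 1 after baseline adjustment; Day 42 effect −0.5 (negative is benefit); Day 28 effect 80% of that; between-visit correlation 0.7; no placebo dropout; in the outcome-related rows, poorer responders on active are likelier to stop. The PPS exclusions for compliance and violations were not simulated. The table gives large-sample bias in SD units with 4 of 16 active stopping, and in brackets the values for 2 of 16 and 5 of 16.

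| Reason for missing data | FAS model | Complete case | Gap at 4/16 |
|---|---|---|---|
| Completely at random | 0.00 | 0.00 | 0.00 |
| MAR: depends on observed Day 28 value | 0.00 | −0.21 (−0.12, −0.26) | −0.21 |
| Not MAR: depends on Day 42 outcome, leaves after Day 28 | −0.16 (−0.09, −0.20) | −0.30 (−0.17, −0.36) | −0.14 |
| Depends on Day 42 outcome, leaves before Day 28 | −0.30 (−0.17, −0.37) | −0.30 (−0.17, −0.37) | 0.00 |
| Stoppers keep no benefit; target is all randomised | −0.12 (−0.06, −0.16) | −0.12 (−0.06, −0.16) | 0.00 |

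Among the rows with outcome-related dropout, the gap is largest where the main model is unbiased and zero where its bias is largest. For the third row at 4 of 16, correlations of 0.5 to 0.9 and weak to strong dropout links give a bias of −0.03 to −0.30 (FAS) and −0.18 to −0.38 (complete case), always with the same sign.

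**Step 3: at the trial's size.** With 16:8 patients and 4 active dropouts, the FAS estimate has an SD of about 0.46 and the gap an SD of 0 to 0.11. In the third scenario the mean gap is −0.272 − (−0.145) = −0.127, little more than its own SD of 0.107. An observed gap could not be read reliably.

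**Step 4: illustration of size.** Suppose k of 16 active patients stop and keep no benefit, stopping is otherwise unrelated to outcome, and the target is the effect in all randomised patients. If E is the effect in those who stay, the target is (1 − k/16) × E while both analyses return E. The overstatement is 1/(1 − k/16) − 1 = k/(16 − k):

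- k = 0: 0%
- k = 1: 1/15 = 7%
- k = 2: 2/14 = 14%
- k = 3: 3/13 = 23%
- k = 4: 4/12 = 33%

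**The case against.** **The analyses are not interchangeable.** A reader might infer that both describe completers and share the same bias. The documents do not support that in general. SAP Table 2 adopts the mixed model in order to use all available data, and a patient with Day 28 but no Day 42 data stays in the FAS fit. The biases coincide only in the cases in the last two rows of the table. This stands, and the point is limited accordingly.

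**Tolerability.** A reader might also infer that missing data will come mostly from patients who tolerated the drug poorly. Protocol 9.8.1 lists many other reasons, dose step-back may keep patients in, and Protocol 6.1.3 reports one adverse-event withdrawal on NLX-112 in a 12-week, 124-patient study at 2 mg/day, in a different population. Against that, Protocol Table 6.1-1 shows drug-related dizziness in 13.2% at 2 mg versus 0.9% on placebo, so tolerability can differ by arm. That is an event rate, not a withdrawal rate. Predominance is unsupported; possibility is enough for the point.

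**Estimand.** If the target is the effect had everyone stayed on treatment, and stopping is unrelated to outcome, neither analysis is biased. The SAP names no estimand, so this stands as a condition on any percentage.

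**Other provisions and status.** SAP 5.9 allows imputation if missing data are substantial, but gives no method or threshold. SAP 5.1 and 5.8 treat efficacy findings as indicative and exploratory, and the primary objective is safety. That lowers the severity without making the check informative. Nor does the SAP say in terms that the run tests MAR. If it is meant only to show the effect of protocol adherence, it is a reasonable supportive analysis, but the complete-case restriction is then unnecessary.

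**Conclusion.** The concern holds in limited form. The complete-case PPS run cannot serve as a check on MAR: it needs a stronger condition than the model it checks, adds post-randomisation selection, and opens no gap when patients leave before their first post-baseline UDysRS. Agreement is not evidence for MAR, and a gap is not evidence against it.

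The 0% to 33% is an illustration for k = 0 to 4, not an estimate for this trial. It rests on an assumed number of stoppers, no retained benefit and a target of all randomised patients, none of which the documents state. The simulated biases rest on the assumed effect, correlation and dropout pattern. This is a cheap improvement to a secondary analysis and does not affect the primary safety objective.

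**What to change.** In SAP 9.2.1, fit the PPS model to all available PPS data, call it supportive, and delete the clause that makes it a validity check.

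For UDysRS total score at Day 42 in the FAS, pre-specify one sensitivity analysis that departs from MAR. Two options are suitable:

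- **Reference-based multiple imputation** for active-arm patients with missing data. Filling in the placebo mean once would understate the variance. In the illustration with k = 4 and an effect of −0.5 SD in those who stay, this targets 12/16 × −0.5 = −0.375 SD.
- **A delta analysis** reporting the shift at which the estimate or its confidence interval reaches no difference. With 4 of 16 missing, each 1 SD of shift moves the estimate by 4/16 = 0.25 SD, so an estimate of −0.5 SD reaches zero at a shift of 2 SD.

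Present the result as exploratory, in line with SAP 5.1 and 5.8. The cost is one extra table and no new data. The estimate may be less favourable, and it will be imprecise because the reference arm has about 8 patients.
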